### 5.5.1.2 RAPID3 analysis

The MDHAQ items that make up the RAPID3 (Routine Assessment of Patient Index Data 3) will be assessed at Baseline and Week 12. The MDHAQ is derived from the HAQ, and the sections that will be utilized are the following:

- MDHAQ-FN : Physical function listed in 10 activities; converted to a scale from 0 to 10 for the RAPID3 score
- MDHAQ-PN : Pain assessed as 0.5 increments from 0 to 10
- MDHAQ-PTGL : Patient's global status assessed as 0.5 increments from 0 to 10
- RAPID3 cumulative score is calculated as the sum (0 to 30) of FN, PN, and PTGL.

RAPID3 analysis will be based on the SS population. By participant list of the MDHAQ-FN (converted scale), MDHAQ-PN, MDHAQ-PTGL and RAPID3 cumulative score with actual values and change from Baseline will be provided at Baseline and Week 12.

### 5.5.1.3 Adverse Events

Adverse events will be recorded from the time of informed consent until study completion. All AEs will be coded and categorized by relationship to CZP. The definitions of TEAE can be found in [Section 5.4.1.2.2](#).

The number and percentage of study participants who experience TEAEs will be for all study participants, SOC, and PT, based on the SS (unless otherwise stated).

Summaries of TEAEs will include the following:

- Summaries of TEAEs will include the following:
  - Incidence of TEAEs (overview including number and percentage of study participants with any TEAEs, serious TEAEs, discontinuations due to TEAEs, drug related TEAEs, severe TEAEs and deaths; event counts will also be included)
- Incidence of TEAEs
- Incidence of TEAEs by maximum relationship
- Incidence of TEAEs by maximum intensity
- Incidence of non-serious TEAEs above threshold of 5% of study participants
- Incidence of non-serious TEAEs above threshold of 5% of study participants by Relationship

Where dates are missing or partially missing, AEs will be assumed to be treatment-emergent, unless there is clear evidence (through comparison of partial dates, see [Section 6.1.6.2](#)) to suggest that the AE started prior to dosing.

Summary tables will contain counts of study participants, percentages of study participants in parentheses and the number of events. A participant who has multiple events in the same SOC and PT will be counted only once in the participant counts, but all events will be included. For the summary of injection site reactions, the specific PTs to be included will be reviewed and documented at the DEM.

In summaries including intensity, the following intensity categories will be summarized: 'Mild', 'Moderate', 'Severe'. Study participants who experience the same event multiple times will be included in the most severe category for tabulations by maximum intensity. Events with missing intensity will be considered as 'Severe' events for summary purposes but recorded as missing in the listings.

In summaries including relationship to CZP, the following relationships will be summarized: 'Not related', 'Related'. Study participants who experience the same event multiple times will be included in the most related category for tabulations by maximum relationship. Events with missing relationship (for CZP) will be considered as 'Related' for the tabulations but recorded as missing in the listings.

A listing will be presented for SS for AEs including TEAE and non-TEAE. This listing will follow the same structure as described in [Section 5.4.1.2.2](#).

#### **5.5.1.4 Vital Signs**

##### **5.5.1.4.1 Vital Sign Values Over Time**

The following vital signs measurements will be collected at Screening visit and End of Study visit (SFU/EDV):

- Pulse rate (bpm)
- Systolic and diastolic blood pressure (mmHg)
- Oral Temperature (°F or °C)
- Respiratory rate (breaths per minute)

Descriptive statistics will be reported for all vital sign for SS. Measured values and changes from Baseline will be summarized by vital signs variables and time point (screening and SFU). Summarization will be as treated, and study participants who missed treatments will not be summarized.

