6.6.1 Dose interruptions

Dose interruptions may only take place due to safety concerns. Participants who have a dose interruption will be followed according to the Schedule of Activities (Section 1.3).

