9.3 Planned safety and other analyses

Safety will be assessed using the SS. Pharmacokinetics and immunogenicity will be assessed using the PKS.

All safety endpoints will be analyzed using descriptive statistics. Safety summaries will include presentations of AEs, laboratory values, and vital signs.

Adverse events will be coded according to the Medical Dictionary for Regulatory Activities. Treatment-emergent AEs will be defined as events that have a start date on or following the first administration of study treatment in RA0138 through the final administration of study treatment +70 days.

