## 4 POPULATIONS FOR ANALYSIS

The following analysis sets will be used in the study:

- All Study Participants (ASP) will include those study participants who are confirmed as having signed the ICF form to participate in the study.
- The Safety Set (SS) will include all study participants enrolled who receive  $\geq 1$  injection of study medication. Safety variables will be summarized using the SS.
- The Pharmacokinetic Set (PKS) is a subset of the SS, consisting of study participants who have provided plasma samples with measurable concentrations (with recorded sampling time) on at least 1 visit, and who have no important protocol deviations affecting the PK parameters.

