#### **5.1.1.2 Protocol Deviations**

Important protocol deviations are deviations from the protocol which potentially could have a meaningful impact on study conduct or on the primary PK outcome for an individual study participant. PK samples outside the protocol windows, missing doses or delayed doses potentially impacting PK, will be reviewed. PK sampling protocol deviations will not automatically cause their exclusion from the PKS set. The table of summary PK statistics and geometric mean PK concentration-time figure will be presented with and without those PK samples determined to be protocol deviations.

The criteria for identifying important protocol deviations will be defined within the appropriate protocol-specific document at study start. Important protocol deviations will be reviewed as part of the ongoing data cleaning process.

Furthermore, overall trends in protocol deviations will be discussed at the Data Evaluation Meeting. Through this data cleaning and evaluation process, all decisions regarding important protocol deviations and exclusions from analysis populations will be made. Important protocol deviations including those that lead to exclusion from the analysis sets will be identified and documented prior to database lock.

All tabulations and listing of protocol deviations will be performed for all study participants.

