##### **5.7.1.5 COVID-19 Impact**

For study participants impacted by the COVID-19 global pandemic, data was collected on a separate eCRF. This form was collected for study visits that were affected by COVID-19, and it collected how the visits were impacted by the pandemic (e.g., performed out of window, done by telephone instead of on-site, not done, etc).

Based on how the visit was affected by the global pandemic, all visits will have following impact categories indicating how the visit was performed:

- Visit not done
- Visit performed out of window
- Home visit
- Missed study drug
- Administration/dispensation
- Temporary discontinuation of study drug
- Termination of study participation
- Other (if other, specify the details)

Additionally, for visits that are affected by COVID-19, all assessments that are missing will be flagged as missing due to COVID-19. Further, the specific reason of missing data will be captured as the following flags:

- Confirmed COVID-19 infection
- Suspected COVID-19 infection
- General circumstances around COVID-19 without infection
- Other

A summary of number and percentage of study participants with COVID-19 impact for all study participants and visit will be provided for the ASP.

A by-site, participant and visit listing of COVID-19 related protocol deviations will be provided including impacted visit and date of impacted visit.

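### The vital-sign summary excludes Safety Set members who 'missed treatments', a term neither document defines; the clause either drops treated participants or does nothing

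*SAP*

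**What the plan says.** SAP 5.5.1.4.1 names the population for the vital-sign table: "Descriptive statistics will be reported for all vital sign for SS". The time points tabulated are Screening and the Safety Follow-up (SFU). The paragraph ends: "Summarization will be as treated, and study participants who missed treatments will not be summarized".

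The SS is everyone enrolled who received at least one injection (SAP section 4; Protocol 9.1). Both sections assign safety to that set without exception; in the SAP, "Safety variables will be summarized using the SS". Protocol 9.3 does the same and counts vital signs among the safety outputs: "Safety summaries will include presentations of AEs, laboratory values, and vital signs".

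Neither document defines a missed treatment. The nearest wording is in two other places. The PK deviation review in SAP 5.1.1.2 says that "missing doses or delayed doses potentially impacting PK, will be reviewed". The COVID-19 visit-impact categories in SAP 5.7.1.5 include "Missed study drug".

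**The concern.** The paragraph names a population and then takes people out of it by a rule that is not defined. It gives no number of doses and no period, and it does not say whether stopping early counts. Two programmers could build different tables from it, and both could claim to have followed the SAP.

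If the clause is applied to missed doses, the loss may be related to safety. Protocol 6.6.1 states: "Dose interruptions may only take place due to safety concerns". It also keeps participants with an interruption on the Schedule of Activities, so they can have SFU vital signs. Some of these interruptions will involve a missed dose. Others may only delay one, which SAP 5.1.1.2 names separately from missing doses. A safety table should not omit such participants by rule.

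**Working it through.** The plan states no figure on this point, so there is nothing to reproduce. The check compares each possible reading of the sentence with the rest of the plan.

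**Inputs**
- SS entry: at least 1 injection (SAP section 4; Protocol 9.1).
- Planned doses: Weeks 0, 2 and 4, then every 2 weeks from Week 6 to Week 24 (SAP 5.1.1.1.3), which is 3 + 10 = 13.
- Planned enrolment: 30, with at least 25 evaluable participants expected to complete Visit 13 at Week 12 (Protocol 1.1; SAP 1.2.2).
- Vital signs collected at Screening and SFU/Early Discontinuation only; no study drug is given at either visit (Protocol 1.3).

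**Readings**
1. *Never treated.* These people are not in the SS, so the clause removes 0 participants and is redundant.
2. *Missed one or more doses.* An SS member has had at least 1 of 13 doses and can miss up to 13 − 1 = 12. Anyone who missed at least one is dropped, contrary to SAP section 4 and Protocol 9.1 and 9.3. SAP 6.2 declares no change from the protocol-planned analyses, so this would be an undeclared departure.
3. *Missed the dose at the tabulated visit.* No dose is due at Screening or SFU, so this reading has no content.

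**Comparison with parallel summaries.** The adverse-event summaries (SAP 5.5.1.3), the chemistry and hematology summaries (SAP 5.5.1.5.2) and the other safety analyses (SAP 5.6) use the SS without this exclusion. No reason is given for treating vital signs differently. The 'as treated' part separates nothing: SAP 5.1.1.3 describes a one-arm study in which misallocation does not apply.

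**Scale**
- Reading 1: 0 removed.
- Reading 2: each participant removed is 1/30 = 3.3% of the planned table. The total would need a missed-dose rate, which the documents do not give, and none is assumed here.
- If early stopping also counted, the only related planning figure is the margin to Visit 13: 30 − 25 = 5, and 5/30 = 16.7%. This is a planning allowance by Week 12 and not a forecast, because participants can be non-evaluable for other reasons and those who withdraw may be replaced (Protocol 9.7).

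**The case against.** The strongest reply is that the sentence is leftover template wording. It opens with 'as treated', follows directly on the SS statement, and can be read as excluding only the untreated. This SAP has other leftovers: it calls for ADA results by treatment group in a one-arm study, and it mentions plots for PD endpoints although none are evaluated. On that view, the absence of the exclusion from the parallel safety sections also points to stray text. This is a fair account of how the sentence may have arisen, but nothing in the documents establishes the harmless meaning. The SAP elsewhere uses similar wording for missed drug in people on study.

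The support from those other places is imperfect. SAP 5.1.1.2 concerns PK. The COVID-19 category may be part of an item split across two lines, since the next bullet concerns administration and dispensation. They show that a missed-dose reading is plausible, not that it was intended.

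The argument about informative loss should also be kept modest. SAP 5.7.1.5 allows for drug missed through general pandemic circumstances, which is not a safety reason. SFU falls 70 days after the last dose, and the documents give no evidence linking a skipped dose to vital signs at that visit. The argument is stronger for early stoppers, whose discontinuation-visit values share the SFU column of the Schedule of Activities, but whether they count as having missed treatments is itself unstated.

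Finally, table shells are not among the documents, so it cannot be checked whether the ambiguity reaches the output.

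**Conclusion.** The concern holds and is minor. Followed as written, the sentence excludes treated SS members from a safety summary that the same paragraph, SAP section 4 and the protocol assign to the whole SS. The only reading that avoids this conflict and still has a meaning makes the sentence superfluous. That the term is undefined and the rule conflicts with the stated population is certain. Whether anyone would actually be dropped is not known: it depends on the meaning intended and on how many doses are missed.

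The effect is confined to one descriptive table at Screening and SFU, for an endpoint in the 'Other' tier. No hypothesis is tested. The by-participant listing in SAP 5.5.1.4.2 covers all study participants, and vital-sign abnormalities judged clinically significant are recorded as adverse events (Protocol Appendix 3).

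**What to change.** In SAP 5.5.1.4.1, replace the whole final sentence with: *All SS participants with a value at the time point will be summarized, regardless of missed or interrupted doses.*

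If the clause was only meant to exclude the untreated, the table's population does not change. If it was not, the new sentence prevents an undeclared exclusion and brings the section into line with SAP section 4 and Protocol 9.1 and 9.3. The cost is one sentence in the SAP, with no extra data collection.

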##### **5.5.1.4.2 Individual Participant Changes of Vital Sign Values**

A by- participant listing of all vital sign measurements and change from Baseline will be presented for all study participants and time point. Body weight will be included in the listing.

### 5.5.1.5 Clinical laboratory evaluations

#### 5.5.1.5.1 Handling of dropouts or missing data

Measurements below the limit of quantification (BLQ) will be imputed with half of the lower limit of quantification (LLOQ) for the lab purpose of calculating change and percentage change from Baseline for summaries and figures. Measurements above the limit of quantification (ALQ), if applicable, will be imputed to the upper limit of quantification.

Descriptive statistics will be calculated if at most 33% of the individual data points at a time point (Visit 13, Week 12 and SFU) are missing or are either not quantifiable (<LLOQ) or ALQ. The denominator for percentages will be based on the number of study participants at corresponding analysis visit for the purpose of the safety analysis. Unscheduled and additional laboratory results will not be summarized but only listed.

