8 STUDY ASSESSMENTS AND PROCEDURES

Study procedures and their timing are summarized in the Schedule of Activities (Section 1.3).

Protocol waivers or exemptions are not allowed. Immediate safety concerns should be discussed with the Sponsor immediately upon occurrence or awareness to determine if the participant should continue or discontinue study treatment.

Adherence to the study design requirements, including those specified in the Schedule of Activities (Section 1.3), is essential and required for study conduct. All Screening evaluations

must be completed and reviewed to confirm that potential participants meet all eligibility criteria. The Investigator will maintain a screening log to record details of all participants screened and to confirm eligibility or record reasons for screening failure, as applicable.

Procedures conducted as part of the participant's routine clinical management (eg, blood count) and obtained before signing of the ICF may be utilized for Screening or Baseline purposes provided the procedures met the protocol-specified criteria and were performed within the time frame defined in the Schedule of Activities (Section 1.3).

The maximum amount of blood collected from each participant over the duration of the study, including any extra assessments that may be required, will not exceed 100mL. Repeat or unscheduled samples may be taken for safety reasons or for technical issues with the samples.

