#### 5.5.1.5.2 Laboratory values over time

Laboratory data (clinical chemistry, hematology, urinalysis and other screening test) and changes from Baseline (if applicable) for numeric variables will be listed for SS and time point. Any laboratory measurements that are BLQ or ALQ will be handled as described in [Section 5.5.1.5.1](#). Values outside the reference range for the numeric variables will be flagged in the listings. The reference ranges will also be reported in the listings.

Chemistry and hematology parameters will be summarized on the SS at each time point, for both absolute values and changes from Baseline.

Laboratory variables will be grouped according to the laboratory function panel and categorized as normal, high or low, if applicable, based on the reference range supplied by the analytical laboratory.

Liver function test elevations should be listed. Potential Hy's Law is defined as a participant with (AST or ALT > 3 x ULN) and TBL > 2 x ULN and ALP < 2 x ULN on the same visit.

In order to meet the above criteria, a participant must experience the elevation in bilirubin and ALT or AST at the same visit. For example, a participant who experiences a  $\geq 2$  x ULN elevation of bilirubin at one visit and a 3 x ULN elevation in ALT (or AST) at a subsequent visit has not fulfilled the Hy's law criteria.

Markedly abnormal laboratory values will generally be defined as those categorized as Grade 3 or higher based on the Rheumatology Common Toxicity Criteria (RCTC) v2.1 (Woodworth et al, 2007). Definitions of markedly abnormal values using the Grade 3 cutpoints are given in the tables below ([Table 5-3](#) for markedly abnormal hematology values and [Table 5-4](#) for markedly abnormal biochemistry values). Any ambiguity about the RCTC criteria was resolved by correspondence with the senior author. In particular, the published Grade 3 cutpoint for lymphocytes (<1.0) was found to be too high, corresponding with the lower limit of normal, and thus was changed to <0.5.

Markedly abnormal laboratory (hematology and biochemistry) values with abnormality flag and Hy's Law will be flagged in laboratory listing together for SS and each time point.

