**Table 5–4 Definitions of Markedly Abnormal Biochemistry Values**

Parameter (SI units)	Markedly Abnormal Definition	
	Low	High
Alkaline Phosphatase	N/A	>3 x ULN
ALT	N/A	>3 x ULN
AST	N/A	>3 x ULN
Calcium (mmol/L)	<1.75	>3.125
CPK	N/A	>4 x ULN
Creatinine	N/A	>1.8 x ULN
Glucose (mmol/L)	<2.22	>13.89
Potassium (mmol/L)	<3.0	>6.4
Sodium (mmol/L)	<125	N/A
Total bilirubin	N/A	≥2 x ULN
Uric acid	N/A	≥3 x ULN

N/A = Not Applicable

Unscheduled visit and duplicate measurement will be handled in [Section 6.1.6.1](#) and baseline definition will be described in [Section 5.1.1.1.5](#).

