### 5.5.1.5.3 Individual Participant Changes of Laboratory Values

For selected laboratory variables that are identified in [Section 5.5.1.5.2](#), the change in category from Baseline will be presented in shift tables at each post-Baseline assessment.

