## **6.1.6 Data derivation rules**

### **6.1.6.1 Handling of repeated and unscheduled measurements**

All repeated and unscheduled measurements will be presented in the listings. Repeated and unscheduled measurements will not be used for statistical analysis or summary tables, unless the repeated measurement was performed due to unreliable values/technical reasons, or the repeated measurement occurred prior to Investigational Medicinal Product (IMP) administration and is defined as the 'baseline'. The following general rules will apply to all repeated and unscheduled measurements:

- For repeated measurements obtained prior to the first dose of IMP the latest reliable value (which may be scheduled or unscheduled) will be used in the calculation of descriptive statistics
- For repeated measurements obtained at the designated Baseline visit, the latest reliable value (which may be scheduled or unscheduled) will be defined as the Baseline. Repeated measurements designated Baseline will be used in descriptive statistics rather than the planned measurement they replace
- For repeated measurements obtained at any time point after the first dose of IMP, the first reliable value of any repeated measurements will be used in the calculation of changes from Baseline and for the descriptive statistics.

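### Non-technical post-dose repeat and unscheduled laboratory results stay out of every laboratory table, and markedly abnormal values are flagged in listings but never counted (minor reporting gap)

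*SAP*

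**What the plan says.** Two SAP rules govern laboratory results taken outside the schedule.

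- SAP 5.5.1.5.1, on laboratory data: "Unscheduled and additional laboratory results will not be summarized but only listed".
- SAP 6.1.6.1, on all measurements: "Repeated and unscheduled measurements will not be used for statistical analysis or summary tables". Two exceptions apply: a repeat made because a value was unreliable or for a technical reason, and a pre-dose repeat that serves as Baseline. For repeats after the first dose, the first reliable value is used, not the worst.

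The text below Table 5-4 ties the two together for laboratory data: "Unscheduled visit and duplicate measurement will be handled in" Section 6.1.6.1.

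The planned laboratory outputs are:

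- Summaries of chemistry and hematology by time point (SAP 5.5.1.5.2).
- Shift tables (SAP 5.5.1.5.3): "the change in category from Baseline will be presented in shift tables at each post-Baseline assessment". Their categories come from SAP 5.5.1.5.2, where variables are "categorized as normal, high or low, if applicable, based on the reference range supplied by the analytical laboratory".
- Listings. Liver test elevations are listed. Markedly abnormal values and potential Hy's Law cases "will be flagged in laboratory listing together for SS and each time point".

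No worst-value or any-time laboratory table appears in the SAP. The Protocol expects off-schedule sampling. Section 8 says "Repeat or unscheduled samples may be taken for safety reasons or for technical issues with the samples", and Appendix 2 (10.2) lets the Investigator order additional tests whenever they are needed.

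**The concern.** Unscheduled safety draws are ordered because something may be wrong, so they are among the likeliest places for an abnormal result to appear. In this study they are also the only laboratory data over long stretches: for a completer, Week 12 is the only scheduled laboratory draw in the 24-week Treatment Period. A rule that keeps these results out of the tables means that a transient abnormality can be measured, confirmed and followed to resolution while every laboratory table shows the participant as normal.

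The SAP also sets explicit thresholds for marked abnormality and then produces no count against them. A reader of the report who wants to know how many participants exceeded, say, three times the upper limit of normal (ULN) for ALT would have to count flags in a listing.

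**Working it through.** No figure in the plan needs reproducing. The check has three parts: the visit arithmetic, a worked case, and a comparison of outputs.

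**Gaps between tabulated draws (completer, nominal days).** Inputs: laboratory assessments at Screening, Week 12 and SFU/EDV (Protocol 1.3); Screening from Day -28 to Day -1 (SAP 5.1.1.1.3); Week 12 = Day 84 and last dose = Day 168 (Protocol 1.3); SFU 70 days after the last dose (Protocol 4.4), or 30 days for participants continuing on commercial drug (SAP 5.1.1.1.3); SFU window ±7 days (Protocol 1.3).

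| Interval | Calculation | Gap |
|---|---|---|
| Screening to Week 12 | 84 − (−1) to 84 − (−28) | 85 to 112 days |
| Week 12 to SFU at 70 days | (168 + 70) − 84 = 238 − 84 | 154 days (147 to 161 with ±7) |
| Week 12 to SFU at 30 days | (168 + 30) − 84 = 198 − 84 | 114 days (107 to 121 with ±7) |

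No safety laboratory draw is scheduled from Day 0 until Day 84.

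**Worked case.** ALT is 4×ULN at an unscheduled safety draw at Week 16 (Day 112) and normal by Week 19 (Day 133). There are no symptoms, and bilirubin and INR are not raised.

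- It is markedly abnormal under SAP Table 5-4 (ALT above 3×ULN).
- Its observed persistence is 133 − 112 = 21 days, short of the 4 weeks (28 days) that Protocol Appendix 6 sets for stopping at 3 to below 5×ULN. This assumes weekly monitoring is possible, since Appendix 6 otherwise stops dosing. Figure 7-1 is not visible in the public copy, so its conditions could not be checked.
- Days 112 to 133 lie between the Week 12 draw (Day 84) and the SFU draw (Day 238, or Day 198). With normal Baseline, Week 12 and SFU values, every shift table reads normal to normal.

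**Where that result appears.**

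| Output | Shows the result? |
|---|---|
| By-time-point summaries | No; excluded by SAP 5.5.1.5.1 |
| Shift tables | No, reading SAP 5.5.1.5.3 with 5.5.1.5.1 and 6.1.6.1 |
| Count of markedly abnormal values | No such table is planned |
| Flagged laboratory listing | Yes |
| TEAE tables | Only if the Investigator judges it clinically relevant (Protocol 8.2.4, Appendix 3) |

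Even if unscheduled draws did enter the shift tables, the normal/high/low categories would not separate 4×ULN from a value just above normal. The mapping of early discontinuation visits (EDV) in SAP 5.1.1.1.4 brings EDV results into the tables but does not cover other unscheduled draws.

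**The case against.** The strongest defence is that this is a deliberate and consistent choice. Tabulating scheduled draws only avoids summaries that depend on how often each participant happened to be tested, and a single-arm study has no comparator to balance that out. Protocol 9.3 promises descriptive presentations of laboratory values, not worst-value tables, so no stated endpoint is left unaddressed. With about 30 participants the flagged listings can be read in full. Clinically relevant changes become adverse events, liver data are listed for suspected drug-induced liver injury (SAP 6.1.3), and meeting a liver stopping criterion triggers 24-hour reporting and a liver event form (Protocol Appendix 6).

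Most of this stands, and it is why the point is minor. It does not supply the missing count. The adverse event route depends on the Investigator's judgment rather than on Tables 5-3 and 5-4, and the cytopenia search in the SAP's table of adverse events of special interest is limited to serious events. Dependence on testing frequency justifies keeping unscheduled values out of by-visit means. It does not rule out a separate, footnoted any-time count.

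It is also fair that SAP 5.5.1.5.3 does not say the shift tables are limited to scheduled visits. That limit is read from the other two sections; it is the likelier reading but not an explicit one.

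Stronger readings should be resisted. A reader might infer that unscheduled results are lost or hidden. They are not: all are listed, and abnormal ones are flagged. A reader might infer that every repeat is excluded, but SAP 6.1.6.1 excepts technical repeats and Baseline values. A reader might also want the share of abnormal episodes missing from the tables. The documents give no rate of unscheduled testing, no episode duration and no onset pattern, so no such share can be derived.

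**Conclusion.** The concern holds as a minor safety-reporting gap. On the current SAP text, non-technical post-dose repeat and unscheduled results are outside all laboratory tables, and markedly abnormal values are defined and flagged but never counted. With tabulated post-dose draws nominally 154 days apart (114 under the 30-day rule), an abnormality detected and resolved between draws is visible only in the flagged listing, unless it is also recorded as an adverse event.

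The consequence is limited. Laboratory assessments fall under Other in the objectives, there is one arm of about 30 participants, collected data remain available, and Cmin and AUC are unaffected. The conclusion rests on two things: reading the shift tables as confined to scheduled and mapped EDV draws, and nominal visit timing. The missing count of markedly abnormal values depends on neither. Changing this is optional but worthwhile.

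**What to change.** Keep scheduled values for the by-visit summaries. In SAP 5.5.1.5.2 and 5.5.1.5.3, add:

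1. A worst post-Baseline column in the shift tables.
2. A table counting participants with any markedly abnormal value, by parameter, using Tables 5-3 and 5-4.

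Both should use all scheduled, EDV, reliable repeat and unscheduled results after the first dose up to and including the SFU Visit. Its +7-day window should be included, so that a draw 71 to 77 days after the last dose is not cut off. State that the exclusions in 5.5.1.5.1 and 6.1.6.1 do not apply to these two outputs.

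The cost is a few lines of SAP text, one column and one table, from results already collected and listed. The downside is that participants tested more often have more chances of an extreme value; a footnote to both outputs should say so. Abnormalities that were never tested for, and local results not entered in the CRF, would still be missed.
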